2.4.3 Extent of investigational medicinal product exposure and compliance

The extent of IMP exposure and compliance will be assessed and summarized by actual treatment within the safety population ([Section 2.3.2](#)) and ABPM substudy population (see [Section 2.3.1.2](#)).

2.4.3.1 *Extent of investigational medicinal product exposure*

The extent of IMP exposure will be assessed by the duration of IMP exposure.

Duration of IMP exposure is defined as

(Date of last double-blind IMP dose) – (date of first double-blind IMP dose) + 1 day,

regardless of unplanned intermittent discontinuations (see [Section 2.5.3](#) for calculation in case of missing or incomplete data).

Duration of IMP exposure will be summarized descriptively as a quantitative variable (number of patients exposed, mean, SD, median, minimum, and maximum). In addition, duration of treatment exposure will also be summarized categorically by numbers and percentages for each of the following categories and cumulatively according to these categories:

- 1 to 28 days
- 29 to 56 days
- 57 to 84 days
- 85 to 126 days
- 127 to 182 days
- 183 to 364 days
- 365 to 551 days
- >551 days

Additionally, the cumulative duration of treatment exposure will be provided, defined as the sum of the duration of treatment exposure for all patients, and will be expressed in patient years.

Number and percentage of patients by final dose at the end of the treatment will also be presented by each treatment group.

2.4.3.2 *Compliance*

A given administration will be considered noncompliant if the patient did not take the planned dose of treatment as required by the protocol. No imputation will be made for patients with missing or incomplete data.

Percentage of compliance for a patient will be defined as the number of days that the patient was compliant divided by the total number of days that the patient was planned to take during the

treatment epoch defined in [Section 2.1.4](#) (ie, from the first date to the last date of double-blind IMP administration).

Above-planned dosing percentage for a patient will be defined as the number of days that the patient took a higher dose than planned divided by the total number of days that the patient was planned to take during the treatment epoch.

Under-planned dosing percentage for a patient will be defined as the number of days that the patient took a lower dose than planned divided by the total number of days that the patient was planned to take during the treatment epoch.

Treatment compliance, above-planned, and under-planned dosing percentages will be summarized descriptively as quantitative variables (number, mean, SD, median, minimum, and maximum). The percentage of patients whose compliance is <80% will be summarized. In addition, numbers and percentages of patients with at least 1 day above-planned dose will be provided, as well as numbers and percentages of patients with (0, 20%], and >20% of days under-planned dose.

Cases of overdose (see study protocol for further details) will constitute AEs/SAEs and will be analyzed as such. More generally, dosing irregularities will be listed in [Section 2.2.1](#).

2.4.4 Analyses of efficacy endpoints

Efficacy analyses will be performed on the ITT population using efficacy assessment collected during the study, including those obtained after IMP discontinuation or introduction of rescue therapy, unless otherwise specified.

Statistical testing will be performed for primary endpoint and some secondary endpoints at Week 26 (or Week 12 for SBP) as specified in the following subsections. All efficacy variables after Week 26 will only be summarized by descriptive statistics without formal statistical testing.

Missing data for efficacy analyses is identified through steps described in [Section 2.5.4](#).

2.4.4.1 Analysis of primary efficacy endpoint(s)

The statistical test will be two-sided at a nominal 5% significance level.

Primary analysis

The primary efficacy endpoint change in HbA1c from baseline to Week 26 will be analyzed by an ANCOVA model using HbA1c values measured at baseline and Week 26 (observed or imputed). The missing data at endpoint will be imputed by multiple imputation (MI) methods in 2 parts as detailed below. To be concise, the following texts related to imputation are generalized to accommodate primary as well as continuous secondary efficacy endpoints.

1. Missing endpoint data for patients who prematurely discontinue the IMP before the Week 26 (or Week 12 for SBP) visit will be imputed using a model built separately in each treatment group and estimated from the patients in the same treatment group who prematurely discontinue the IMP before the Week 26 (or Week 12 for SBP) visit but have

the measurement for the endpoint (retrieved dropouts). Considering that the number of patients in each treatment group who discontinue the IMP but have the measurement for the endpoint is expected to be small, a simple imputation model based on regression will be used with baseline measurement included as the predictor. Each treatment group will have their own imputation model.

2. Missing endpoint data for all patients who stay on the IMP until the Week 26 (or Week 12 for SBP) visit, including those in the sotagliflozin 400 mg group, will be imputed separately. The wash-out imputation method will be used, where missing endpoint data in the sotagliflozin 400 mg group, as well as in the placebo group are imputed from a model estimated from patients in the placebo group who stay on the IMP until the Week 26 (or Week 12 for SBP) visit and have the endpoint data available. The imputation model will include the randomization strata and the corresponding baseline value. Missing data will be imputed using the regression method.

An alternative (back-up) imputation method will be used if the number of patients who prematurely discontinue the IMP before the Week 26 (or Week 12 for SBP) visit but have the measurement for the endpoint is <5 in any treatment groups (ie, not sufficient retrieved dropouts to support the imputation method described above). This criterion will be assessed for each primary or continuous secondary efficacy endpoint separately.

In the back-up imputation method, missing post-baseline values will be imputed by control-based copy reference MI method under the missing not at random (MNAR) framework.

- For placebo patients, missing data will be imputed based on the placebo group data,
- For patients in the sotagliflozin 400 mg group, missing data will be imputed as if the patients were on placebo throughout the study, where all patients' measurements including the on-treatment measurements will be considered as if the measurements were from the placebo group in the imputation model.

Using either imputation method, missing endpoint data will be imputed multiple times to generate multiple data sets with complete data (see sample code Part 1a or Part 2a of Appendix B). The change from baseline to Week 26 will be derived from observed and imputed HbA1c values at Week 26. Each of the completed datasets after the imputation will be analyzed using the ANCOVA model with the treatment groups (sotagliflozin 400 mg, placebo), randomization stratum of HbA1c ($\leq 8.0\%$, $> 8.0\%$), randomization stratum of SBP (< 130 , ≥ 130 mmHg), and country as fixed factors, and baseline HbA1c value as a covariate (see sample code Part 4 of Appendix B). The results from each analysis will be combined using Rubin's formula, to provide the adjusted mean change in HbA1c from Baseline to Week 26 for each treatment group, as well as its between-group difference (comparing sotagliflozin 400 mg vs placebo) and the corresponding 95% confidence interval (CI) for the difference (see sample code Part 5 of Appendix B).

Sensitivity analyses

Tipping point analysis based on the same MI method as applied to the primary analysis will be performed to examine the robustness of the results from the primary analysis. Patients who were randomized to sotagliflozin 400 mg group and had no HbA1c data at Week 26 will be given a

penalty. The penalty will be gradually increased to evaluate at which level the conclusion of the analyses in terms of statistical significance is changed. The tipping point is the penalty level, at which the magnitude of efficacy reduction in patients without HbA1c data at Week 26 creates a shift in the treatment effect of sotagliflozin 400 mg from being statistically significantly better than placebo to a non-statistically significant effect. LS mean difference between sotagliflozin 400 mg and placebo and its associated p-value will be provided for each penalty level. The steps to perform the tipping point analysis are as follows:

1. Missing data will be imputed using the same MI method as applied to the primary analysis (see sample code Part 3 in Appendix B),
2. The imputed HbA1c value at Week 26 in the sotagliflozin 400 mg group will be penalized by adding a penalty δ (eg, $\delta = 0.1\%$) in each complete dataset (see sample code Part 3 in Appendix B),
3. Change from Baseline at Week 26 in HbA1c will be analyzed using the same ANCOVA model as specified in the primary analysis in each complete dataset (see sample code Part 4 in Appendix B),
4. Results will be combined across complete datasets using Rubin's rule (see sample code Part 5 in Appendix B),
5. Steps 2 to 4 will be repeated with incremental penalty at δ (ie, $\delta, 2\delta, 3\delta$, etc) until the p-value for treatment effect of sotagliflozin 400 mg compared to placebo estimated in Step 4 is >0.05 .

The tipping point analysis will be performed only if the primary variable (Change from Baseline to Week 26 in HbA1c) is statistically significant at $\alpha = 0.05$ (2-sided).

If the retrieved dropout imputation is applied to the primary analysis, the analysis based on the control-based imputation (ie, the backup imputation method) will be presented as a sensitivity analysis.

Assessment of treatment effect by subgroup

Descriptive analyses will be performed on the primary endpoint to summarize the treatment effects across subgroups defined by the following Baseline or Screening factors:

- Race (White, Black or African American, Asian, Other) (any race groups with fewer than 5 patients may be combined with "Other" category as appropriate),
- Ethnicity (Hispanic, Not Hispanic),
- Age group ($<50, \geq 50$ to $<65, \geq 65$ years) (any category with fewer than 5 patients may be combined with another category as appropriate),
- Gender (Male, Female),
- Baseline BMI level ($<30, \geq 30 \text{ kg/m}^2$),
- Baseline HbA1c ($\leq 8.0\%, >8.0\%$),
- Baseline HbA1c ($\leq 8.5\%, >8.5\%$),

- Baseline mean SBP (<130 mmHg, ≥ 130 mmHg),
- Baseline eGFR (≥ 30 to <60 mL/min/1.73 m² [Moderate decrease in GFR], ≥ 60 to <90 mL/min/1.73 m² [Mild decrease in GFR], and ≥ 90 mL/min/1.73 m² [Normal]),
- Duration of diabetes (<10 , ≥ 10 years),
- Country.

The treatment effects across the subgroups defined above will be estimated for the Change from Baseline to Week 26 in HbA1c in the ITT population using the same MI method as applied to the primary analysis. The ANCOVA model will include treatment (sotagliflozin 400 mg, placebo), randomization stratum of HbA1c ($\leq 8.0\%$, $>8.0\%$), randomization stratum of SBP (<130 , ≥ 130 mmHg), subgroup factor, treatment-by-subgroup factor, and country as fixed factors and baseline HbA1c as a covariate (see sample code Part 4 of Appendix B). The adjusted estimates of treatment mean differences (sotagliflozin 400 mg versus placebo) with standard error (SE) and 95% CIs will be provided as appropriate across the subgroups. A graphical presentation of the results (ie, forest plot) will also be provided.

In the case that the subgroup factor is identical or similar to a randomization strata factor (eg, baseline HbA1c or baseline mean SBP category), only the subgroup variable (as single factor or an interaction term) will be included in the model in order to avoid the issue of collinearity in the analysis. The corresponding strata factor will not be included in the model.

Summary statistics at scheduled visits

Summary statistics (for screening value, baseline value, observed post-baseline value and its Change from Baseline) at scheduled visits will be provided for each treatment group. The summary will include the number of observations, mean, SD, standard error (SE), minimum, median, and maximum. Graphical presentations will also be used to examine trends over time using mean values (\pm SE) and mean changes from baseline (\pm SE) at each of the scheduled visits.

Similar presentations will be provided excluding measurements after rescue therapy during the entire 79-week double-blind treatment period.

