In case of permanent discontinuation of the treatment with IMP before Week 26 and/or Week 79, every effort will be made to have the patient return to the site at the time of their Week 26 and Week 79 visits; however the MMTT should not be performed at these or any other visit following a Premature EOT visit.

On the days of the MMTT, patients will come to the investigational site in the morning, in fasting conditions for at least 8 hours and must not eat any food or drink, except water, before the scheduled standardized meal test.

The exact times of the IMP administration, standard mixed liquid breakfast meal intake, and the blood draws are to be documented.

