10.1.3.2 On-site Visit 13 at Week 79 - End-of-treatment

The following will be performed at this visit:

- IRT to be notified (if EOT visit is also last visit, IRT should be notified for end of study)
- IMP accounting and compliance
- Patient diary, including hypoglycemia log, is collected/reviewed and dispensed and instructions/training are provided as needed
- Concomitant medications are assessed
- AEs/SAEs/AESI/EOSI and hypoglycemia (if any) are reported
- Patients are evaluated for glycemic rescue (see [Section 9.1.4.7](#))
- Measurement of body weight
- Complete physical examination including vital signs (SBP and DBP, temperature, heart rate, and respiratory rate). Three separate seated BPs and heart rate measurements should be taken with at least 1 minute between measurements following a 5-minute rest period, and prior to phlebotomy (see [Appendix E](#) for details of BP procedure)
- Diet and exercise instruction is provided
- Instruction on DKA symptoms (see [Appendix D](#)) is provided
- Instruction on basic GU hygiene and hydration (see [Appendix D](#))
- 12-lead ECG, prior to the morning IMP administration
- Fasting SMBG is assessed

- Standard MMTT (2-hour post prandial glucose measurements)(not to be performed if patient has discontinued prior to Premature EOT visit; see [Section 10.3.4](#))
- The following laboratory testing (by the central laboratory):
 - Fasting plasma glucose
 - HbA1c
 - Urine pregnancy testing for WOCBP (any positive urine test results must be confirmed by a serum pregnancy test)
 - Hematology
 - Clinical chemistry to include amylase and lipase
 - Fasting lipids
 - Urinalysis (dipstick and microscopy)
 - Urine analysis for albumin, calcium, glucose, and creatinine
- Additional laboratory testing at this visit:
 - Markers of intestinal transit and absorption (vitamins B6, B12, K, E, and A, serum folate, and ferritin)
 - Markers of bone and calcium metabolism (serum and urinary calcium, serum 25-hydroxyvitamin D, serum 1,25-dihydroxyvitamin D, serum and urinary phosphorus, serum PTH, markers of bone resorption [serum NTX, serum β -CTX-1], and bone formation [serum P1NP])

- Plasma concentration samples (pre-dose and 2 hours 30 minutes post-dose) are collected and sent to the appropriate laboratory (this is not necessary if the patient discontinued study treatment early)
- Patients are instructed to return to the site in 4 weeks for Visit 14.

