10.3.3 List of criteria for permanent treatment discontinuation

The patients may withdraw from treatment with the IMP at any time for any reason or this may be the Investigator's decision. Patients should discuss stopping study medication with the site before doing so in order that questions can be addressed, glycemic therapy adjusted, and a follow-up assessment arranged. All efforts should be made to document the reasons for treatment discontinuation and this should be documented in the e-CRF.

The following reasons lead to permanent discontinuation:

- At the patient's own request (ie, withdrawal of consent for treatment)
- If, in the Investigator's opinion, continuation with the administration of the study treatment would be detrimental to the patient's well-being
- Inter-current condition that requires permanent discontinuation of the study treatment as long as the abnormality persists and if the causal relationship of the concerned event and the IMP is possible (according to the Investigator's best medical judgment)
- Pregnancy (in female patients)
- Specific request of the Sponsor.

Any abnormal laboratory value will be immediately rechecked for confirmation before making a decision of permanent discontinuation of the IMP for the concerned patient.

For patients who prematurely discontinue the IMP, the assessments planned at EOT visit (Section 10.1.3.2) will be performed at the Premature EOT Visit, scheduled preferably prior to treatment discontinuation or as soon as possible after time of discontinuation (the latest at the next on-site visit). Reason for IMP discontinuation will be clearly specified. This Premature EOT assessment may occur at a regularly scheduled visit or at an unscheduled visit.

Patients participating in the ABPM substudy will not be required to discontinue the substudy in the event that they permanently discontinue treatment in the main study. Every effort should be made to ensure that discontinued patients complete the ABPM substudy, if they are willing and able to do so.

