2.4.4.2 Analyses of secondary efficacy endpoints

For continuous secondary endpoints with missing data at baseline, missing data will be imputed using MI under the missing at random (MAR) assumption. Missing data at baseline will be imputed using regression method that includes randomization stratum of HbA1c ($\leq 8.0\%$, $>8.0\%$), randomization stratum of SBP (<130 , ≥ 130 mmHg), and baseline value in the imputation model (see sample code Part 1b or Part 2b in Appendix B).

The continuous secondary endpoints (Section 2.1.3.2) will be analyzed using similar ANCOVA model including corresponding measurements at baseline and endpoint (observed or imputed) as described in Section 2.4.4.1. The missing data at endpoint will be imputed by the retrieved dropouts & washout imputation method or by the control-based copy reference imputation method according to the criterion described in Section 2.4.4.1. After imputation, each of the complete

datasets will be analyzed by an ANCOVA model with treatment groups (sotagliflozin 400 mg, placebo), randomization stratum of HbA1c ($\leq 8.0\%$, $> 8.0\%$), randomization stratum of SBP (< 130 , ≥ 130 mmHg), and country as fixed effects, and corresponding baseline value as a covariate. For the analysis of SBP in patients with baseline SBP ≥ 130 mmHg, the randomization stratum of SBP will not be included in the ANCOVA model. Results from each complete dataset will be combined using Rubin's formula to provide the adjusted mean Change from Baseline to Week 26 (or Week 12 for SBP) for each treatment group, as well as the between-group difference (comparing sotagliflozin 400 mg vs placebo) and the 95% CI for the difference.

For all continuous secondary endpoints, summary statistics at scheduled visits will be provided for each treatment group. The summary will include the number of observations, mean, SD, SE, minimum, median, and maximum. Graphical presentations will also be used to examine trends over time using mean values (\pm SE) and mean changes from baseline (\pm SE) at each of the scheduled visits. In addition, SBP will be summarized descriptively at each visit for those with baseline SBP ≥ 140 mmHg.

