2.5.4 Windows for time points/Measurements for analyses

The following steps will decide how the scheduled and/or unscheduled visits will be used in efficacy analyses and by-visit summary analyses for safety variables (clinical laboratory data in [Section 2.1.4.4](#) and vital signs in [Section 2.1.4.5](#)).

Step 1 A scheduled measurement will be used if it is available; otherwise, an unscheduled measurement (including the end of treatment/study visit for those prematurely discontinued) will be used if it happens to be on the same date as the date of the scheduled visit.

Step 2 After Step 1, if there are still no measurement for a given parameter at a scheduled visit, the analysis window below ([Table 4](#)) will be applied to re-allocate a post-baseline unscheduled measurement to a scheduled measurement.

Table 4 - Analyses window definition

Scheduled visit post baseline	Targeted study day	Analysis window in study days
Week 1 (Visit 4)	7	2 to 17
Week 4 (Visit 5)	28	18 to 41
Week 8 (Visit 6)	56	42 to 69
Week 12 (Visit 7)	83/84	70 to 104
Week 18 (Visit 8)	126	105 to 153
Week 26 (Visit 9)	181/182	154 to 227
Week 39 (Visit 10)	273	228 to 318
Week 52 (Visit 11)	365	319 to 409
Week 65 (Visit 12)	455	410 to 502
Week 79 (Visit 13)	551	>502

Study days are calculated from the day of first administration of double-blind IMP; the day of first administration of IMP (or the day of randomization if not exposed) is Day 1.

After applying above visit windows, if multiple assessments are associated to the same time point, the closest from the targeted study day will be used. In case of equality, the last measurement will be used. Re-allocated scheduled visits (ie, visit number) should be sequential if ordered by the date of measurement.

After Step 2, if there are still no measurement for a given parameter at a scheduled visit, data is considered missing for efficacy analyses, where multiple imputation would be applied as appropriately as described in [Section 2.4.4](#).

For ABPM substudy, an analysis window of 70 to 133 was used for Visit 7A, and 134-227 for Visit 9A.

Reference day

The reference day for the calculation of extent of exposure, time to onset, and relative days will be the day of the first administration of double-blind IMP or the day of randomization if not exposed to double-blind IMP, denoted as Day 1.

Baseline definition for efficacy/safety data

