Appendix B Sample SAS® code for analyses of efficacy endpoints

```

* VARIABLES;
* treat - treatment;
* strata1 - stratification factor 1;
* strata2 - stratification factor 2;
* value0 - value at baseline;
* value1 ... valuen - value at each post-baseline visit for a total of n visits; valuen for the endpoint visit;
* change - change from baseline;

*****;
*****Part 1: Preferred imputation method: the retrieved dropouts and washout imputation ****;
*****;

/* Part 1a, for parameters with no missing data at baseline */;

* MI in patients who prematurely discontinued IMP before the endpoint using the endpoint data from its own group (retrieved dropouts);
proc sort data=ads;
  by treat ptid;
run;
proc mi data=ads out= disc_mi nimpute=2000 seed=97531;
  where discontinue = "Y";
  by treat;
  var value0 valuen;
  monotone regression (valuen = value0 );
run;

* MI in patients who stay on the IMP until the endpoint visit using the endpoint data from the placebo group (wash-out MI);
proc sort data=ads;
  by ptid;
run;
proc mi data=ads out= comp_mi nimpute=2000 seed=75319;
  where discontinue="N" and (treat=1 or (treat ne 1 and valuen = . )); *1 denotes placebo group;
  class strata1 strata2;
  var strata1 strata2 value0 valuen;
  monotone regression (valuen = strata1 strata2 value0 );
run;

* Repeat dataset with the same number of replications for remaining patients who have complete data at the endpoint visit;
data comp_trt;
  set ads (where=(discontinue="N" and treat ne 1 and valuen ne .));
  _imputation_=0;
  do i = 1 to 2000;
    _imputation_=imputation_+1;
    output;
  end;

```

```
run;

* Combine three subsets of patients;
data mi_1;
    set disc_mi comp_mi comp_trt;
run;

/*Part 1b, for parameters with missing data at baseline */

* Impute the missing data at baseline;
proc sort data=ads;
    by ptid;
run;

proc mi data=ads out=mi_base n impute=2000 seed=13579;
    class strata1 strata2;
    var strata1 strata2 value0;
    monotone regression;
run;

* MI in patients who prematurely discontinued IMP before the endpoint using the endpoint data from its own group (retrieved dropouts);
proc sort data=mi_base;
    by _imputation_ treat ptid;
run;

proc mi data=mi_base out= disc_mi n impute=1 seed=97531;
    where discontinue = "Y";
    by _imputation_ treat;
    var value0 valuen;
    monotone regression (valuen = value0 );
run;

* MI in patients who stay on the IMP until the endpoint visit using the endpoint data from the placebo group (wash-out MI);

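### For 2-hour PPG the meal-test rules leave only on-drug values as retrieved-dropout donors, so patients who stopped treatment may be imputed as if still on it

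*SAP*

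**What the plan says.** **Imputation rule.** SAP 2.4.4.1 imputes missing values of patients who stopped IMP before the endpoint visit, separately by arm, from a regression on baseline "estimated from the patients in the same treatment group who prematurely discontinue the IMP before the Week 26 (or Week 12 for SBP) visit" and who do have the endpoint value. These are the retrieved dropouts. If an arm has fewer than five, a control-based copy-reference method replaces it; this is judged for each endpoint separately. SAP 2.4.4.2 covers all continuous secondaries, including 2-hour PPG: missing data "will be imputed by the retrieved dropouts & washout imputation method or by the control-based copy reference imputation method". Neither the text nor Appendix B Part 1a requires a donor's value to be taken after the last dose; the code selects on the discontinuation flag alone.

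**Visit windows.** SAP 2.5.4 counts as unscheduled measurements those "including the end of treatment/study visit for those prematurely discontinued". If the scheduled value is absent, a window "will be applied to re-allocate a post-baseline unscheduled measurement to a scheduled measurement". For Week 26 it is Days 154 to 227.

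**Meal test.** After permanent discontinuation the patient is asked back at Week 26, "however the MMTT should not be performed at these or any other visit following a Premature EOT visit" (Protocol 9.1.4.2). Protocol 10.1.3.2, whose assessments are also used at the Premature EOT visit, says the test is "not to be performed if patient has discontinued prior to Premature EOT visit". Under Protocol 10.3.3 those assessments "will be performed at the Premature EOT Visit, scheduled preferably prior to treatment discontinuation", or otherwise soon afterwards. Appendix C bars the test during a temporary interruption.

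**Testing order.** PPG is the first test after HbA1c, and a failure stops the sequence (SAP 2.4.4.5).

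**The concern.** Retrieved dropouts are meant to show what happens to patients after they stop. For PPG they cannot. If the meal-test rules are followed, a patient who stops before Week 26 has a usable PPG value only if a meal test was done, still on drug, at a Premature EOT visit on Day 154 or later. Such values qualify as donors and count toward the five-donor criterion. If both arms reach five, PPG for everyone else who stopped is drawn from a handful of on-drug values, which assumes no loss of effect after stopping.

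No planned analysis would show how much this matters. The control-based sensitivity analysis in SAP 2.4.4.1 is for the primary endpoint. Appendix G lists no supportive analysis for PPG. The additional analyses in SAP 1.6 use the same donor definition. At stake are the precision and meaning of the PPG estimate and, through the fixed sequence, access to the later tests.

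**Working it through.** **The plan's own figures.** None is given for PPG. Protocol 11.1 plans HbA1c with 250 per arm, difference 0.6%, SD 1.2%: power = Φ(0.6/(1.2·√(2/250)) − 1.96) = Φ(5.59 − 1.96) ≈ 0.9999, which agrees with the stated at least 99%. Its ratio, 0.6/1.2 = 0.5 SD, serves below only as a reference effect. Discontinuation rate, stop times, PPG effect and PPG SD are not in the documents and are assumed.

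**Step 1: donors allowed.** Off-drug donors permitted under Protocol 9.1.4.2 and 10.1.3.2 together: none. On-drug donors must fall between Day 154 and the Week 26 visit (Day 182): 28/182 = 15% of the core period (14 to 17% over the ±3-day visit window).

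**Step 2: chance that both arms reach five.** Let d be discontinuation by Week 26, with stop times uniform, and s the share of in-window stoppers with an on-drug meal test. Expected donors per arm = 250 × d × (28/182) × s. At s = 1 this is 3.85/5.77/7.69 for d = 10/15/20%. Chance = [P(Binomial(250, d × (28/182) × s) ≥ 5)]². At s = 1 the single-arm probabilities are 0.341/0.686/0.885; squared, 0.116/0.470/0.783.

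| Share tested on drug | d = 10% | d = 15% | d = 20% |
|---|---|---|---|
| half | 0.2% | 3% | 12% |
| three quarters | 3% | 19% | 47% |
| all | 12% | 47% | 78% |
| all, but only 10% of stops in window | 1% | 10% | 32% |

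**Step 3: consequence when triggered.** Simulation: 250 per arm; 25/37/50 discontinuers per arm, of whom 6/7/8 are donors (close to the means of 6.0/7.0/8.3 given at least five, at s = 1); baseline correlation 0.4; Bayesian regression on baseline; 100 imputations; ANCOVA on treatment and baseline; Rubin's rules; no strata or country. The comparator imputes from placebo data. That is in effect what copy-reference does here, since PPG is measured only at Day 1, Week 26 and Week 79.

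| d = 10/15/20% | Retrieved dropouts | Placebo-based |
|---|---|---|
| Mean SE (SD units) | 0.116/0.129/0.143 | 0.085/0.087/0.089 |
| Power at 0.35 SD | 87/80/72% | 98/96/94% |
| Power at 0.5 SD | 99/98/95% | 100% |
| Rejection under the null | 2.6/2.8/3.0% | 3.5/3.1/2.1% |

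The larger SE arises because an intercept, a slope and a residual variance are estimated from six to eight patients. Letting donor counts vary, given at least five, lowers retrieved-dropout power further: 80/71/64% at 0.35 SD and 97/92/88% at 0.5 SD.

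**Step 4: size of the estimate.** With an on-drug effect E and every in-window stopper tested, the missing share is m = d × (1 − 28/182) = 0.085/0.127/0.169. The retrieved-dropout estimate is about E and the back-up's about E(1 − m). The first exceeds the second by 1/(1 − m) − 1 ≈ 9/15/20%. If half the effect persists after stopping, the true value is E(1 − m/2). The current rule is then high by 1/(1 − m/2) − 1 ≈ 4/7/9%, and the back-up is low by the same percentages, since (1 − m)/(1 − m/2) − 1 ≈ −4/−7/−9%.

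**The case against.** The strongest reply is that the SAP largely handles this already. It expects few donors, and its five-donor rule, applied to PPG on its own, leads to the very method proposed here. That stands, and at about 10% discontinuation the back-up is the likely outcome.

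The all-tested row is also optimistic. No main-study visit falls between Week 18 (Day 126) and Week 26. A Premature EOT visit may follow stopping, as late as the next on-site visit, which would then be Week 26 itself, with no meal test. The rows for half and three quarters deserve more weight.

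Nor is accuracy a clear gain. With half the effect retained, the two methods miss by similar amounts in opposite directions. The effect of 0.35 SD, where the power loss is large, has no source in the documents. And the SAP does fix its method and switching rule in advance, so lack of prespecification is not the complaint.

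It could also be called uneven to bar these values as donors yet keep them as observed Week 26 results. That has less force: SAP 2.5.4 treats late Premature EOT values this way for every endpoint, and using a value as a patient's own result differs from using it to stand for others who have stopped.

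A reader might infer that the protocol flatly contradicts itself on the meal test. The documents do not go that far. Appendix C's provision for an earlier test concerns patients leaving the study; Protocol 9.1.4.2 concerns patients who stop IMP and return for visits. What remains is that Appendix C sets no on-drug condition, and that flow chart footnote j and Protocol 10.1.3.2 refer to Protocol 10.3.4, which does not mention the meal test.

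**Conclusion.** The point holds in a conditional form. For PPG the retrieved-dropout step either does not run or, if the meal-test rules are followed, runs on on-drug values only. Off-drug donors could arise only from tests done against those rules or from the Appendix C provision for patients leaving the study.

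When triggered with 6/7/8 donors per arm, the SE rises to about 0.12/0.13/0.14 SD from 0.09. Power falls by about 1 to 5 points at 0.5 SD and about 10 to 25 points at an assumed 0.35 SD, and by more if donor counts vary. The estimate sits about 9 to 20% above the back-up's. All these sizes rest on the assumptions listed above.

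Three stronger readings are tempting but unsupported:
- That PPG will be imputed from on-drug values. That needs five donors in both arms, which is unlikely unless discontinuation is well above 10% and most in-window stoppers are tested on drug.
- That the false-positive rate rises. Simulated null rejection stays below 5%.
- That HbA1c, FPG, body weight or SBP share the problem. No such bar applies to them, and off-drug values are sought at scheduled visits after stopping.

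The benefit of a change is precision, and an imputation that does not treat stopped patients as on drug. It is not a demonstrably less biased estimate. The correction is worth making because it is specific and cheap.

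**What to change.** - **SAP 2.4.4.2:** state that missing 2-hour PPG goes directly to the control-based copy-reference method (code in Appendix B Part 2). State also that on-drug Premature EOT PPG values are neither donors nor counted toward the five-donor criterion, but remain observed values under SAP 2.5.4.
- **SAP 1.6:** apply the same exclusion, so that its wash-out back-up is used for PPG.
- **Minor clarification:** reconcile Protocol 9.1.4.2, 10.1.3.2 and Appendix C on the meal test after early stopping, and correct the cross-references to Protocol 10.3.4.

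No change is needed for HbA1c, FPG, body weight or SBP.

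The cost is two SAP sentences, one line in SAP 1.6 and the clarification. The code exists, and Protocol 11.4.2.2 already named control-based imputation for the secondaries. The downside is a smaller PPG point estimate, by about 8 to 17% (the missing share m in Step 4), in the cases where the current rule would have been triggered.
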